12.7.2. Handling of Missing Data

Element	Reporting Detail
General	
 Missing data occurs when any requested data is not provided, leading to blank fields on the collection instrument: 
 These data will be indicated by the use of a "blank" in participant listing displays. Unless all data for a specific visit are missing in which case the data is excluded from the table. Answers such as "Not applicable" and "Not evaluable" are not considered to be missing data and should be displayed as such.
Outliers	
 Any participants excluded from the summaries and/or statistical analyses will be documented along with the reason for exclusion in the clinical study report.

12.7.2.1. Handling of Missing and Partial Dates

Element	Reporting Detail
General	
 Partial dates will be displayed as captured in participant listing displays.
Adverse Events	
 The eCRF allows for the possibility of partial dates (i.e., only month and year) to be recorded for AE start and end dates; that is, the day of the month may be missing. In such a case, the following conventions will be applied for calculating the time to onset and the duration of the event: 
 Missing Start Day: First of the month will be used unless this is before the start date of study treatment; in this case the study treatment start date will be used and hence the event is considered On-treatment as per Appendix 4: Study Phases and Treatment Emergent Adverse Events. Missing Stop Day: Last day of the month will be used, unless this is after the stop date of study treatment; in this case the study treatment stop date will be used. Completely missing start or end dates will remain missing, with no imputation applied. Consequently, time to onset and duration of such events will be missing.
Concomitant Medications/	
 Partial dates for any concomitant medications recorded in the CRF will be imputed using the following convention: 
 If the partial date is a start date, a '01' will be used for the day and 'Jan' will be used for the month 
 If the partial date is a stop date, a '28/29/30/31' will be used for the day (dependent on the month and year) and 'Dec' will be used for the month. The recorded partial date will be displayed in listings.

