7.1.1. Adverse Event Summary Measures

AE data will be summarised in tables and figures by the following:

- Part A by randomised treatment;
- Parts A, B and follow-up by randomised treatment;
- Parts A, B and follow-up by period treatment (i.e. treatment participant actually received).

AE data will be presented in data listings by the following:

- Parts A, B and follow-up by period treatment (i.e. treatment participant actually received).

Table 3 Overview of Planned Adverse Event Analyses

Endpoint / Parameter/ Display Type	Absolute		
	Summary		Individual
	T	F	L
Adverse Events (AEs)			
All AE by Maximum Intensity by SOC and PT	Y		
All Drug-Related AEs by Maximum Intensity by SOC and PT	Y		
Common ($\geq 10\%$) AEs / Drug-Related AEs by Overall Frequency	Y	Y ^[1]	
Common ($\geq 10\%$) Non-serious AEs by SOC and PT (Number of Subjects and Occurrences)	Y		
All AEs	Y		Y
Subject Numbers for Individual AEs			Y
Relationship Between AE SOCs, PT & Verbatim Text			Y
Serious and Other Significant AEs			
Serious AEs by SOC and PT (Number of Subjects and Occurrences)	Y		
Fatal Serious AEs			Y
Non-Fatal Serious AEs			Y
AEs Leading to Permanent Discontinuation of Study Treatment or Withdrawal from Study	Y		Y
Reasons for Considering as a Serious AE			Y
Possible Suicidality-Related AE (PSRAE)			Y

NOTES:

- T = Table, F = Figures, L = Listings, Y = Yes display generated, SOC = System Organ Class, PT = Preferred Term.
 - Summary = Represents TF related to any summaries (i.e. descriptive statistics) of the observed raw data.
 - Individual = Represents L related to any displays of individual participant observed raw data.
- 1: Plot of common AEs and relative risk will be generated.

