			Day 1	Day 8 (±3)	Day 15 (±3)	Day 22 (±3)	Day 29 (±3)	Day 36 (±3)	Day 43 (±3) (week 6)	Day 50 (±3)	Day 57 (±3)	Day 64 (±3)	Day 71 (±3)	Day 78 (±3)			Day 85 (+2) (week 12)
Urine pregnancy test (WCBP only) ¹²			X ⁴		X		X		X ⁴		X		X		X	X	X
Haematology, chemistry, urinalysis	X		X ⁴		X		X ¹³		X ⁴		X ¹³		X ¹³		X	X	X
Faecal calprotectin ¹⁴		X	X		X		X		X		X		X		X	X	
Blood sample for exploratory biomarkers and TE ¹⁵			X ⁴						X ⁴						X	X	
PK blood samples GSK2982772 ¹⁶			X						X ⁴						X	X	
Biopsies for PK, inflammatory biomarkers, mRNA, TE & pathway marker analysis		X-----X ⁷							X ⁴						X	X ⁸	
Pharmacogenetic sample (PGx) ¹⁷			X														

Footnotes:

1. Full medical history (includes past and current conditions, medication history, substance usage, and family history of premature CV disease).
2. Full physical exam (includes height/weight at screening, height not measured at later time points).
3. Triplicate ECG to be performed at screening only and if stopping criteria are met.
4. Pre-dose.
5. Any SAEs assessed as related to study participation (e.g., protocol-mandated procedures, invasive tests, or change in existing therapy) or related to a GSK product will be recorded from the time a participant consents to participate in the study up to and including any follow-up. AEs will be collected from the start of Study Treatment until the follow-up contact.
6. PRO assessments should be conducted before any tests, procedures or assessments to avoid influencing the participants' perception.

7. Sigmoidoscopy may be performed at any time during the screening window as an additional visit (if required) up to Day -7 in order for central reading confirmation of Mayo Score for inclusion. If a shorter window is required (e.g., within Day -3 to Day -7), this will be permitted as long as it has been confirmed with the sponsor and central reader that results of the Mayo endoscopy score will be available before end of screening window. Histological disease (e.g., UCEIS, MRS and Geboes Index) along with Mayo score assessments will also be completed.

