12.4. Appendix 4: Study Phases and Treatment Emergent Adverse Events

12.4.1. Study Phases

Treatment phases will be defined for Part A and Part B of the study. Therefore, assessments and events will be classified according to the time of occurrence relative to study treatment start date and the Day 43 visit.

Study Phase	Definition
Pre-Treatment	Date ≤ Study Treatment Start Date
On-Treatment	Study Treatment Start Date < Date ≤ Study Treatment Stop Date
On-Treatment (Part A)	Study Treatment Start Date < Date ≤ Day 43 Visit Date
On-Treatment (Part B)	Day 43 Visit Date < Date ≤ Study Treatment Stop Date
Post-Treatment	Date > Study Treatment Stop Date

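### The AE start-day imputation is bounded only by the first treatment start, so day-missing AEs from the crossover month always fall in Part A and day-missing events from a month before treatment become On-treatment

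*SAP*

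**What the plan says.** SAP 12.7.2.1 lets the eCRF hold AE dates as month and year only. For a missing start day, "First of the month will be used unless this is before the start date of study treatment"; if it is before, "in this case the study treatment start date will be used and hence the event is considered On-treatment as per Appendix 4". The only bound is the single study treatment start date.

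Appendix 4 (12.4.1) states that "assessments and events will be classified according to the time of occurrence relative to study treatment start date and the Day 43 visit". Part A is "Study Treatment Start Date < Date ≤ Day 43 Visit Date" and Part B is "Day 43 Visit Date < Date ≤ Study Treatment Stop Date", so the Day 43 visit date itself belongs to Part A. Section 12.4.2 has a separate AE flag: Pre-Treatment if onset is strictly before treatment start, On-Treatment from the start date to one day after the stop date. It has no Part A/Part B split.

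Section 7.1.1 plans AE tables for Part A by randomised treatment, for the whole study by randomised treatment, and for the whole study by the treatment actually received in each period. By footnote 5 of the schedule (12.2.1), AEs are collected from the start of study treatment. SAEs related to study participation or a sponsor product "will be recorded from the time a participant consents to participate in the study up to and including any follow-up".

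**The concern.** The start-day rule suits a trial with one treatment start. This trial has two, because all Part A completers begin open-label drug at Day 43. An AE known only to have begun in the crossover month may have started before or after that change, and the rule always decides for before. For a participant randomised to placebo, this labels a possible drug-period event as placebo in the tables meant to show treatment actually received.

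The rule also never checks that the recorded month is the treatment-start month before moving the date forward. An event whose month rules out on-treatment onset is still called On-treatment, although 12.4.2 keeps a Pre-Treatment category for it.

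Adverse events are a primary endpoint. The period-treatment AE tables are 3.3, 3.6, 3.9, 3.12, 3.15, 3.18, 3.21 and 3.24. The Part A-only tables, from 3.1 to 3.22, are the only placebo-controlled AE summaries.

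**Working it through.** The SAP gives no figure on this point, so there is none to reproduce. The check applies its rules to every possible calendar position.

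**Inputs.** Imputation rule: 12.7.2.1. Phase boundaries: 12.4.1. AE flag: 12.4.2. Day 43 visit window ±3 days and a screening period of up to 30 days: 12.2.1 and 2.3. Randomisation of about 36 participants 2:1, taken as 24:12: 2.3. Assumptions: last dose on Day 84, and onset spread evenly over days.

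**Crossover month, by reasoning.**
- The imputed date is the 1st of the month containing the Day 43 visit, which is never after that visit. If the visit is on the 1st, the two dates coincide, and 12.4.1 still gives Part A.
- The treatment-start bound never applies. The earliest visit (Day 40) is 39 days after Day 1, so the two cannot share a calendar month. The earliest study day the 1st can be is 43 − 30 = 13, or 40 − 30 = 10 at the early end of the window.
- The imputed date is therefore always after treatment start and no later than the Day 43 visit, which is Part A.

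**Crossover month, by enumeration.** 1,461 start dates (four calendar years) × 7 visit offsets = 10,227 schedules.
- A day-missing AE from the crossover month falls in Part A in 10,227 of 10,227.
- Part B days re-assigned to Part A when the day is missing: 150,640 of 419,307 = 35.9%. Per schedule this is 150,640 / 10,227 = 14.7 days on average (range 0 to 30), out of 419,307 / 10,227 = 41.0 Part B days.
- True Part A days re-assigned to Part B: 0. The error runs one way.
- Share of crossover-month days after the Day 43 visit: 48.4%. The other 51.6% fall on or before it.

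**Prior month.** Over the same schedules and a 30-day screening period, 156,170 of 10,227 × 30 = 306,810 screening days (50.9%) lie in a month before the treatment-start month. A day-missing event from any of these is re-dated to treatment start. All 156,170 are then On-Treatment under 12.4.2, and all 156,170 are Pre-Treatment under 12.4.1, whose Pre-Treatment phase includes the start date. The two tables disagree.

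**Example.** First dose 10 March 2018, Day 43 on 21 April 2018.
- An AE dated April 2018 becomes 1 April (study day 23), Part A, even if it began on 22–30 April.
- An SAE dated February 2018 becomes 10 March. If it resolved on 20 February, the 12.4.2 duration is 20 February − 10 March + 1 = −17 days.

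**Size of one event.** In the period-treatment tables with full completion, the placebo column has 12 participants and the drug column 24 + 12 = 36. One re-assigned event can add 1/12 = 8.3 points to placebo and remove 1/36 = 2.8 points from drug. These tables count subjects, so the gain needs no other event of that term in the participant's Part A, and the loss needs none in Part B.

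**The case against.** **The imputation is only for onset time and duration.** The rule is introduced so that "the following conventions will be applied for calculating the time to onset and the duration of the event". But its next step carries the imputed date into Appendix 4, and the SAP has no other rule for assigning a day-missing AE to a part. This objection does not stand.

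**Few events are involved.** This stands. The SAP gives no count of partially dated AEs, and participants record AEs on diary cards with calls between visits. As an illustration, assume 12 Part B AEs in the placebo-randomised participants, of which 1% to 5% lack a start day: 12 × 0.01 × 0.36 = 0.04 to 12 × 0.05 × 0.36 = 0.22 events.

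**Affected events can be seen.** Listings show partial dates as captured, so they can be found. That does not correct the tables, and it leaves the choice of column until after unblinding.

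**The rule is not less accurate than its opposite.** Also true: slightly more than half of crossover-month days are Part A. The objection to the rule is its direction, not its error rate.

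**Stronger readings to avoid.** A reader might infer that the rule masks a drug signal in every AE table. It does not. In the Part A-only tables it also moves active-arm Part B events into active Part A, and that arm has about twice as many participants. The whole-study tables by randomised treatment do not depend on the split. A reader might also infer that any AE from before treatment becomes On-treatment, but ordinary AEs are not collected then. Nor does the SAP settle that a re-dated SAE enters the Part A SAE table (3.19), because 12.4.1 calls that date Pre-Treatment.

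**Conclusion.** The point holds in two parts, both from rules the SAP states rather than from detail it omits.

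1. A day-missing AE from the month of the Day 43 visit always goes to Part A, with no exception for a crossover on the 1st. About 36% of Part B days (14.7 on average) are exposed, given even onset and a last dose on Day 84. Only in the period-treatment tables, and only for participants randomised to placebo, does this put a drug-period event under placebo. There the direction is non-conservative. The 8.3-point effect is per event and conditional on the subject having no other Part A event of that term.
2. A day-missing event from a month wholly before treatment is called On-treatment against its own recorded month. This is limited to SAEs related to study participation or a sponsor product. The 50.9% is a share of screening days, not of events.

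The number of affected events is unknown and probably small. The correction is still worth making: the data pattern is foreseen by the eCRF, and with about 12 placebo participants a single event is visible.

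**What to change.** Replace the start-day rule in 12.7.2.1 with:

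- (a) Recorded month before the treatment-start month: keep the event Pre-Treatment.
- (b) Recorded month equal to the treatment-start month: use the treatment start date. Align 12.4.1 with 12.4.2 so that an event on that date is On-treatment in both.
- (c) Recorded month equal to the crossover month, in the period-treatment tables: classify the AE as Part B (active) unless its recorded stop date is before the first open-label dose. Imputing the first open-label dose date alone changes nothing, because that dose is given at the Day 43 visit and 12.4.1 puts that date in Part A. Either set the AE boundary between the parts by the first open-label dose, or flag the event directly as Part B.
- (d) Otherwise: use the 1st of the month.

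For the Part A-only comparison, apply one convention equally to both arms, and footnote the affected events or show them under both assignments.

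Cost: SAP wording and a few lines of derivation code, to be settled before unblinding. Downside: about half of crossover-month days are truly Part A, so (c) charges some placebo-period AEs to drug in the period-treatment tables, which is the conservative direction for safety.

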2.4. Statistical Analyses

The primary objective of the study is to investigate the safety and tolerability of GSK2982772 60mg tid following 12 weeks of treatment. No formal statistical hypotheses will be conducted to assess this objective.

If appropriate, comparisons between the GSK2982772 arm and the placebo arm will be made to investigate the secondary pharmacodynamic, mechanistic and efficacy objectives. Trends over time will be investigated for both treatment arms along with associations between each of the parameters.

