17. A PGx blood sample is collected at the baseline visit (Day 1), after the participant has been randomized and provided informed consent for genetic research. If the sample is not collected at the baseline visit, it can be collected at any time during the study after randomization.
18. Visit windows during the treatment period are relative to Day 1.
19. If a participant withdraws from the study, every effort will be made for the participant to complete an Early Withdrawal visit prior to the Follow Up visit.
20. Follow-up visit should be completed 28 days (± 3 days) after the last dose of study medication.

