12.4.2. Treatment Emergent Flag for Adverse Events

Treatment State	Definition
AE = Pre-Treatment	If AE onset date is before treatment start date: = AE Onset Date < Study Treatment Start Date
AE = On-Treatment	If AE onset date is on or after treatment start date and on or before treatment stop date: = Study Treatment Start Date ≤ AE Start Date ≤ Study Treatment Stop Date +1
AE = Post-Treatment	If AE onset date is after the treatment stop date: = AE Start Date > Study Treatment Stop Date +1
AE Onset Time Since 1 st Dose (Days)	If Treatment Start Date > AE Onset Date: = AE Onset Date - Treatment Start Date If Treatment Start Date ≤ AE Onset Date: = AE Onset Date - Treatment Start Date +1 Missing otherwise.
AE Duration (Days)	AE Resolution Date – AE Onset Date + 1
AE = Drug-related	If relationship is marked 'YES' on Inform/CRF OR value is missing.

NOTES:

- If the study treatment stop date is missing, then the AE will be considered to be On-Treatment.

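### Capping a missing AE stop day at the treatment stop date gives zero or negative durations when onset follows treatment stop, and contradicts a recorded stop month later than the treatment-stop month

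*SAP*

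**What the plan says.** SAP Section 12.7.2.1 covers AE dates with month and year recorded but the day missing. A missing stop day becomes month-end, "unless this is after the stop date of study treatment; in this case the study treatment stop date will be used". The section gives the purpose: the "conventions will be applied for calculating the time to onset and the duration of the event". A date that is missing altogether is not imputed.

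Section 12.4.2 defines AE duration as "AE Resolution Date – AE Onset Date + 1". It also makes post-treatment events a category of their own, with the condition "AE Start Date > Study Treatment Stop Date +1".

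Section 12.2.1, footnote 5, sets the collection period: "AEs will be collected from the start of Study Treatment until the follow-up contact". Footnote 20 places that contact well after dosing ends: "Follow-up visit should be completed 28 days" (±3 days) after the last dose. Section 7.1.1 plans AE tables, figures and listings that cover follow-up as well as Parts A and B.

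**The concern.** The cap would suit a study that stopped recording AEs at the last dose. This study does not stop there. An event that begins in follow-up cannot have resolved by treatment stop, yet the rule assigns it that date. An event that begins on treatment and is recorded as ending in a later month is moved back out of the month the site entered.

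This is a stated rule that returns impossible values for a foreseeable class of records; it is not a detail left open. Nothing else in Section 12.7.2.1 or 12.4.2 repairs it. There is no requirement that the imputed stop be on or after onset, and no exception where the recorded stop month is later than the treatment-stop month. A programmer who follows the text will produce these values.

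**Working it through.** **Inputs**
- Imputed stop date = the earlier of month-end of the recorded stop month and the treatment stop date (Section 12.7.2.1).
- Duration = stop - onset + 1 (Section 12.4.2).
- Follow-up length F = 28 days, range 25 to 31 (Section 12.2.1, footnote 20). The treatment stop date is taken to be the date of last dose.

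The SAP gives no figure of its own to reproduce.

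**Onset after treatment stop.** Let T be the treatment stop date and T + k the onset date used, with k at least 1. Resolution is on or after onset, so month-end of the resolution month is later than T and the cap always applies.

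Duration = T - (T + k) + 1 = 1 - k

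| k (days after treatment stop) | Duration under the rule |
|---|---|
| 1 | 0 |
| 2 | -1 |
| 10 | -9 |
| 28 | -27 |

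With F between 25 and 31 the minimum runs from 1 - 25 = -24 to 1 - 31 = -30.

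Enumeration confirms this. Taking every treatment stop date in one year, every onset from T + 1 to T + 28 and every resolution from onset to T + 28 gives 365 × (28 × 29 / 2) = 148,190 combinations. Of these, 10,220 gave a duration of zero, 137,970 a negative duration and none a positive one.

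At k = 1, Section 12.4.2 still classes the event as on-treatment, because that window runs to treatment stop + 1. So an event that the SAP calls on-treatment can have a duration of 0.

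**Onset on treatment, recorded stop month later than the treatment-stop month.** If the event truly resolves r days after T, the rule assigns T and removes r days. Example with T = 10 March, onset 1 March and true resolution 5 April, recorded as April:
- True duration: 36 days.
- Under the rule: 10 March - 1 March + 1 = 10 days, so 26 days are lost.
- Even without knowing the day, the earliest date consistent with April is 1 April, 22 days after the imputed date.

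For resolution within a 28-day follow-up the loss lies between 1 and 28 days.

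**Start day also missing.** Section 12.7.2.1 then sets onset to the first of the month. Where that falls on or before T, the duration is positive, though it still ends at a stop date before the event began. This happened for about 52% of the enumerated follow-up onsets at F = 28. The zero or negative result is therefore certain only when the onset date used is after T.

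**With the cap moved to T + F.** No zero or negative duration arises in any of the 148,190 combinations at F = 28, nor in the 118,625 at F = 25 or the 181,040 at F = 31. In the March–April example the imputed stop becomes 7 April and the duration 38 days, against a true 36.

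**The case against.** The strongest objection is about consequence. AEs are a primary endpoint (Section 2.2), so a reader might infer that a primary safety result is distorted. The documents do not support that. No duration endpoint is named. Nothing in Table 3 (Section 7.1.1), the AE tables of Section 12.10.5 or the AE figures of Section 12.10.6 is titled as a summary of duration; they deal with incidence, intensity, relatedness, seriousness and discontinuation. The treatment-emergent flags use onset, so the stop-date cap cannot reclassify an event. Partial dates are listed as captured, so the site's entry stays visible. On the primary objective the SAP says "No formal statistical hypotheses will be conducted to assess this objective". All of this stands and limits the point.

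A reader might also infer that every follow-up AE is affected. Events with complete dates or with wholly missing stop dates are not.

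Finally, a reader might say that every on-treatment event with a partial stop date is truncated. When the recorded stop month is the same as the treatment-stop month, the true date may lie on either side of the last dose. The cap is then arguable, and month-end may overstate duration. Shortening can be shown from the record only when the recorded month is later.

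None of this rescues the rule for onset after treatment stop or for a later recorded stop month.

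**Conclusion.** The rule is wrong as written, with a narrow effect. For an AE with stop month and year recorded, stop day missing and the onset date used k days after treatment stop, the derived duration is 1 - k days. For an on-treatment AE with a recorded stop month later than the treatment-stop month, the imputed date contradicts the record and the duration is too short, by up to 28 days for resolution within a 28-day follow-up.

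The damage is confined to the derived duration variable and any listing that shows it. The listing shells are not reproduced in the SAP (Section 12.11), so whether duration is printed cannot be settled from the document. The SAP gives no frequency of partial dates; with approximately 36 participants planned, the number of affected records may be small or nil, which is an expectation and not a documented figure. The values -27 and 28 days are extremes that need events at the very end of follow-up. This is a minor correction, worth making because the formula cannot give a valid answer in these cases.

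**What to change.** Replace the stop-day sentence in Section 12.7.2.1 with a rule to this effect: a missing stop day is set to the last day of the recorded month, capped at the date of study completion, withdrawal or follow-up contact instead of the treatment stop date, and never earlier than the AE onset date used in the calculation.

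The cost is one sentence and a matching change in the derivation program. No new data are needed, and no other planned analysis changes.

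There is one trade-off to accept knowingly. Events that in fact resolved early in the treatment-stop month will get longer imputed durations. With treatment stop on 10 March, an event from 1 to 5 March recorded as ending in March would be 31 days instead of 10, against a true 5. This is the month-end convention the SAP already applies when month-end falls on or before treatment stop.
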